 - Worsening of CKD, defined as when a subject with CKD Stage 1 or higher defined by NKF guidelines worsens to higher CKD stages (eGFR ≥ 90 with albuminuria at Baseline decreases to < 90 , or eGFR 60 to 89 at Baseline becomes < 60 , or eGFR 30 to 59 at Baseline becomes < 30 mL/min per 1.73 BSA) during treatment
 - Regression of CKD, defined as when a subject with CKD Stage 1 or higher at Baseline improves to normal or lower stages by NKF guideline (eGFR ≥ 90 with albuminuria at Baseline improves to eGFR ≥ 90 without albuminuria, or eGFR 60 to 89 at Baseline becomes eGFR ≥ 90 with or without albuminuria, or eGFR between 30 to 59 at Baseline improves to > 60 mL/min per 1.73 BSA) during treatment
- Serum creatinine:
 - Doubling of serum creatinine concentration, defined as when a subject's creatinine value is at least 2 times the Baseline value and ≥ 1.5 mg/dL during treatment
- Serum cystatin C:
 - Serum cystatin C will be measured to estimate eGFR in the population of subjects who are in CKD Stage 1 or 2 at Baseline. CKD Stage 1 or 2 is defined as albuminuria and eGFR > 60 mL/min per 1.73 BSA

Additional diabetes-related microvascular complications will be assessed by monitoring AEs associated with retinopathy and neuropathy . (revised per Amendment 01)

The following parameters related to NAFLD will be measured: aspartate aminotransferase (AST), alanine aminotransferase (ALT), alkaline phosphatase, gamma glutamyl transpeptidase (GGT), total and direct bilirubin

Obesity-related complications that are not assessed by any of the objective measures listed in this protocol may be evaluated using data from AE reporting, changes in concomitant medications, or reports of changes in medical history. (revised per Amendment 01)

BIOMARKER ASSESSMENTS

The following inflammatory biomarkers will be assessed to further define the CV risk study population and to investigate potential correlation with changes in CV risk factors, MACE, and MACE+, as well as weight loss and susceptibility to diabetes:

- hsCRP will be measured at the time of Screening and will be followed up yearly through EOT.
- Fibrinogen will be measured at the time of randomization and will be followed up yearly through EOT.
- For subjects who provide consent, other biomarkers related to obesity, diabetes, CV disease, and associated risk factors will be evaluated in serum and plasma samples in selected countries, where applicable (see [Appendix 5](#)).

PHARMA GENOMIC ASSESSMENTS

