- b. Assessments are only to be performed if clinically indicated or necessary due to state controlled substance requirements. (revised per Amendment 01)
- c. Window ±10 days for all visits after Visit 2, other than the EOS visit which has a window of +10 days. Month is shown unless otherwise indicated; 1 month = approximately 30 days.
- d. Only for a subset of subjects at selected sites. Baseline echocardiograms will be performed in between Visits 1 and 2, after the results of screening assessments have been obtained but prior to randomization, and subject eligibility is confirmed. ECHOs will be performed until at least 1000 subjects have completed the Month 36 echocardiographic assessment. (revised per Amendment 02)

Table 4 Schedule of Procedures/Assessments in Study APD356-G000-401

Phase	Pre-randomization	Randomization																		
Period	Screening	Treatment																	F/U	
Visit	1	2 ^a	3	4	5	6	7	8	9	10	11	12	13	14	15	16	17	EOT	EOS	Unsch ^b
Month ^c	Days -30 to -1	Day 1	3	6	9	12	15	18	21	24	28	32	36	40	44	48	52	56		
Assessment (revised per Amendment 01)																				

- e. For subjects who discontinue study drug early, these assessments will be stopped after the EOT visit.
- f. Renal function parameters and glycemic profile should be obtained at all specified visits, regardless of study drug status. (revised per Amendment 01)
- g. Serum cystatin C will be measured at Baseline and yearly thereafter in the subpopulation with CKD Stage 1 or 2 at Baseline. Serum creatinine will be measured in chemistry blood samples if chemistry assessments are performed.
- h. Serum pregnancy tests will be conducted at Screening. A urine pregnancy test will be conducted at randomization.
- i. These assessments should be done if a telephone contact is performed in lieu of a clinic visit.

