## 5.4.3 Secondary Endpoint Analyses

For the following endpoints, a Cox proportional hazards model with factors for treatment and stratification variable (presence of established CV disease or CV risk factors without established CV disease) will be used. The estimate of the hazard ratio of lorcaserin HCl to placebo and the corresponding 2-sided 95% CI will be calculated. See Section 8.5 for details on censoring algorithms for the time-to-event endpoints.

The secondary endpoints are considered as supportive analysis to the primary endpoints and key secondary endpoint, therefore no correction for Type I error rate will be performed.

- The time-to-event of each component of MACE+. The Total Time Analysis Set will be used as the primary analysis. The On-Treatment Analysis Set and the On-Treatment plus 30 Days Analysis Set will be used as sensitivity analyses.
- Time-to-event of all-cause mortality. The Total Time Analysis Set will be used as the primary analysis. The On-Treatment Analysis Set and the On-Treatment plus 30 Days Analysis Set will be used as sensitivity analyses.
- Time-to-event of new onset renal impairment or worsening existing renal impairment in all subjects. The ITT Analysis Set will be used for this analysis. (revised per Amendment 02)
- Time-to-event of new onset renal impairment or worsening existing renal impairment in subjects with T2DM at Baseline. The T2DM Analysis Set will be used for this analysis.
- Time-to-event of new onset renal impairment or worsening existing renal impairment in subjects with prediabetes at Baseline. The Prediabetes Analysis Set will be used for this analysis. (revised per Amendment 01)
- Time-to-event of improvement in renal function. The T2DM Analysis Set will be used for this analysis.
- Time-to conversion to T2DM in subjects without any type of diabetes at Baseline.
   The Nondiabetes Analysis Set will be used for this analysis. (revised per Amendment 01)
- o Time to conversion to normal glucose homeostasis (HbA1c ≤5.6% and fasting plasma glucose <100 mg/dL without any antidiabetic treatment). The Prediabetes Analysis Set will be used for this analysis. (revised per Amendments 01 and 02)

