#### 8.2 DETERMINATION OF RENAL IMPAIRMENT OR IMPROVEMENT

### 8.2.1 Determination of new onset or worsening of Renal Impairment

Time from randomization to first occurrence of 2 consecutive assessments within the same component of the composite endpoint or time to first occurrence of renal transplant or renal death, on scheduled or nonscheduled visits at least 30 days apart, indicative of new onset renal impairment or worsening of existing renal impairment (first occurrence of any of the following events: microalbuminuria, macroalbuminuria, worsening albuminuria, newly developed CKD or worsening of CKD, or doubling of serum creatinine, or any of the following: ESRD, renal transplant, renal death). Table 4 presents the definitions for each of these events and Appendix 13.2 presents the definition of Chronic Kidney Disease (CKD) stages.

Table 4 Definitions of new	1 1 1	• •	1
Lobio / Hotinitions of nov	IN CONDON OF	WARRANINA AT RANG	I impoirment avents
Table 4 Delillions of new	iv develon or	WOLSEILING OF LEUX	i illiliali illelli evellis
THE I Delimitions of her	i, action or	" or seming or rema	

Renal Impairment Event	Definition
Newly Developed Albuminuria	For subjects without any microalbuminuria (ACR ≥ 30 μg/mg in spot urine), or macroalbuminuria(ACR ≥ 300 μg/mg in spot urine) at baseline or subject shows first evidence of;  • microalbuminuria (ACR ≥ 30 μg/mg in spot urine) with an ACR value increased ≥ 30% from Baseline  or  • macroalbuminuria(ACR ≥ 300 μg/mg in spot urine) with an ACR value increased ≥ 30% from Baseline
Worsening albuminuria	microalbuminuria present at Baseline and develops macroalbuminuria, and ACR value increases ≥30% from baseline assessment during treatment
Newly develop CKD	eGFR ≥ 90 mL/min per 1.73 body surface area (BSA) and without kidney damage at Baseline changes to CKD Stage 1 or higher classified by the 2002 National Kidney Foundation (NKF) guidelines, where kidney damage referred to in the guideline is defined as the emergence of microalbuminuria as defined above, during treatment
Worsening of CKD	CKD Stage 1 or higher defined by NKF guidelines worsens to higher CKD stages (eGFR ≥ 90 with albuminuria at Baseline decreases to < 90, or eGFR 60 to 89 at Baseline becomes <60, or eGFR 30 to 59 at Baseline becomes < 30 mL/min per 1.73 BSA) during treatment
Doubling of serum creatinine	creatinine value is at least 2 times the Baseline value and ≥ 1.5mg/dL during treatment

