#### 8.5.2.3 Censoring for Secondary Time-to-Event Endpoints

The censoring algorithm is the same for all secondary time-to-event endpoints and across the different Analysis Sets. Since all the Analyses Sets used the ITT population for these secondary endpoints, then for subjects who experienced an event, their time-to-event will be determined from the randomization date to the date of the event. The censoring variable will be, CENSORED=0. For subjects who do not experienced an event, the censoring time will be determined from the randomization date to the date described in Table7, along with a matching censoring variable, CENSORED=1.

Table 7 Censoring Date for Subjects who did not Experience an Event at Study Completion for Secondary Renal and Clucose Homeostasis Endnoints

Secondary Renal and G	lucose Homeo	stasis Endpoints	
	Analysis		Withdrawal From Study Follow-
Time-to-Event Endpoint	Set a	Completed the Study	up
New onset of renal	T2DM	In the Final Study	In the Final Study Disposition
impairment or		Disposition Form use the	Form use the date from, Date of
worsening of existing		date from;	Final Sponsor
renal impairment in		Date of Final Sponsor	Notification/Premature Study
subjects with T2DM at		Notification/Premature	Discontinuation
Baseline		Study Discontinuation	and
New onset of renal	Total Time	and status is equal to	status for discontinuation equals
impairment or		completed	any of the following;
worsening of existing			Withdrew Consent
renal impairment in all			Lost to Follow up
subjects enrolled in the			Study Terminated by Sponsor
study			• Death
Improvement in renal	T2DM		• Other
function	12DNI		
Tunction			
New onset of renal	Prediabetes		
impairment or	riediabetes		
worsening of existing			
renal impairment in			
subjects with			
prediabetes at Baseline			
Conversion to normal	Prediabetes		
glucose homeostasis	1 iculaucies		
a See Section 5.2.1 for det	finitions of An	alvsis Sets	1
500 50000011 5.2.1 101 del	11111110110 01 7 1111	11 J D 10 D D 0 0	

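### Most renal event definitions in the SAP are limited to an undefined treatment period, which conflicts with the ITT-based analysis, follow-up to final disposition and off-drug renal sampling

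*SAP*

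**What the plan says.** **Event definitions.** Four rows of SAP Table 4 carry the limit:

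- worsening albuminuria: "microalbuminuria present at Baseline and develops macroalbuminuria, and ACR value increases ≥30% from baseline assessment during treatment"
- newly developed CKD, where kidney damage is "defined as the emergence of microalbuminuria as defined above, during treatment"
- worsening of CKD, whose last limb reads "or eGFR 30 to 59 at Baseline becomes < 30 mL/min per 1.73 BSA) during treatment"
- creatinine doubling: "creatinine value is at least 2 times the Baseline value and ≥ 1.5mg/dL during treatment"

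The rows for newly developed albuminuria, ESRD, renal transplant and renal death do not. SAP 8.2.2 puts the limit on both regression of albuminuria and regression of CKD. Protocol 9.5.1.4 uses it for all six of these definitions and also for newly developed albuminuria.

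**Analysis and follow-up.** For the all-subjects renal endpoint, SAP 5.4.3 states "The ITT Analysis Set will be used for this analysis". The other renal endpoints use the T2DM and Prediabetes sets, which are subsets of ITT. SAP 8.5.2.3 adds "The censoring algorithm is the same for all secondary time-to-event endpoints and across the different Analysis Sets", and Table 7 ends event-free follow-up at the final-disposition date, not at last dose. Table 7 labels the all-subjects endpoint Total Time. SAP 5.2.1 and 8.5 define Total Time as counting events both on and off drug.

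**Data collection.** Protocol Table 4, footnote f: "Renal function parameters and glycemic profile should be obtained at all specified visits, regardless of study drug status".

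**Definition of the phrase.** There is none. SAP Section 8 defines being on treatment, but only for the On-Treatment and On-Treatment plus 30 Days sets. The renal endpoints use neither.

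**The concern.** The event rule and the follow-up rule point in different directions, and nothing in either document says which prevails. One programmer could read the phrase as on study drug and drop confirmed off-drug events. Another could read it as post-baseline and keep them. Both could defend the choice, and the event counts would differ.

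Under the on-drug reading, a subject who has stopped drug stays in the risk set to final disposition but can have an event only through the unrestricted components. That analysis is not a clean ITT estimate, because collected events are dropped. It is not a clean on-treatment estimate either, because off-drug time is kept. Events are lost in both arms. If the arms stop drug at different rates, they are lost unequally and the hazard ratio shifts.

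**Working it through.** **No figure to reproduce.** The documents give no event count, rate, power or sample size for any renal endpoint, and no drug-discontinuation rate. The 5% annual dropout in SAP Section 4 is study dropout. The size below is therefore an illustration.

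**Inputs from the documents.** 12,000 subjects, 1:1; 15-month accrual; 54-month end; 5% annual dropout.

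**Assumptions.** Constant renal hazard *h* of 3%, 6% or 10% per year. Constant annual drug-stopping rate *d*, independent of renal outcome: 10% on placebo and 10% to 20% on lorcaserin. A share *q* of the renal hazard counts only on drug.

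**Formulas, per arm.**

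- Event-free and on drug: S_on(t) = exp(−(h+d)t)
- Event-free and off drug: S_off(t) = d[exp(−(h+d)t) − exp(−h(1−q)t)] / [h(1−q) − (h+d)]
- S = S_on + S_off; counted events: f = h·S_on + h(1−q)·S_off
- Weight for dropout and staggered entry: w(t) = exp(−0.05t)·min(1, (4.5−t)/1.25)
- The large-sample Cox estimate θ solves ∫ w[f₁ − (f₀+f₁)·θS₁/(S₀+θS₁)] dt = 0
- Events = 6,000·∫ w(f₀+f₁) dt

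**Equal stopping (10% v 10%).** θ = 1.00 for every *q*. Events counted:

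| *h* | *q* = 0 | *q* = 0.5 | *q* = 1 |
|---|---|---|---|
| 3% | 1198 | 1102 | 1002 |
| 6% | 2268 | 2094 | 1905 |
| 10% | 3520 | 3264 | 2971 |

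At 6% the loss is (2268 − 2094)/2268 = 7.7% for half restricted and (2268 − 1905)/2268 = 16.0% for all restricted. The other two rows give 8.0% and 16.4%, and 7.3% and 15.6%.

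**Unequal stopping, true HR 1.00, *h* = 6%.** Apparent HR, lorcaserin to placebo:

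| Stopping, lorcaserin v placebo | *q* = 0.25 | *q* = 0.5 | *q* = 1 |
|---|---|---|---|
| 12% v 10% | 0.993 | 0.985 | 0.965 |
| 15% v 10% | 0.982 | 0.963 | 0.916 |
| 20% v 10% | 0.967 | 0.930 | 0.843 |

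Values at 3% and 10% hazard differ by at most 0.001. If placebo stops more, the arms swap and the ratio inverts: at 15% v 10%, 1/0.963 = 1.04 and 1/0.916 = 1.09.

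**Consequence at 15% v 10%, *h* = 6%, 12,000 subjects.** The two-sided rejection rate with no true effect is 0.07, 0.14 and 0.47 for *q* = 0.25, 0.5 and 1, against 0.05. A true HR of 1.10 appears as 1.08, 1.06 and 1.01.

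**Which column applies.** The worsening composite has unrestricted components, so *q* is below 1. Much newly developed CKD would also be caught through the unrestricted albuminuria row. The improvement endpoint has only restricted components, so *q* = 1. There an HR below 1 means less improvement, so the arm that stops more looks worse.

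**With all components counted (*q* = 0)** the apparent HR equals the true HR in every scenario.

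**Not modelled.** Protocol 9.4.5.1 has drug temporarily discontinued when eGFR below 30 persists on repeat, and the endpoint needs two assessments at least 30 days apart. For a fall from 30–59 to below 30, the confirming value may therefore often be taken off drug. This bears on counting only, and no size is attached to it.

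**The case against.** The best defence is that the phrase simply means post-baseline. Treatment is also the name of the study period that covers the visits to Month 56, and subjects who stop drug keep attending those visits. The ITT-based sets, the Total Time label, Table 7 censoring and footnote f all favour counting off-drug events. In the albuminuria definitions the phrase sits next to the ACR change and may not limit event timing at all. This stands to the extent that literal on-drug programming cannot be taken as the plan's settled rule. It does not remove the conflict: the phrase is undefined, and it appears on some components and not on others.

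A reader might infer more: that all off-drug time counts as event-free, and that lorcaserin is made to look renally safer. The documents do not support this. Four components remain countable off drug. The Section 8 definition of off treatment is confined to sets that the renal endpoints do not use. A between-arm bias needs both literal programming and unequal discontinuation, and no per-arm rates are given. For the improvement endpoint the direction is the opposite.

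**Conclusion.** The concern holds as an unresolved contradiction between the renal event definitions and the plan's own analysis sets, censoring and data collection, with components of one composite under different counting rules. Any bias is conditional. If the limit is programmed literally, about 8% to 16% of events are lost at an assumed 10% annual discontinuation with half to all of the hazard restricted, and the HR is about unbiased when the arms stop equally. With no true effect, the HR is about 0.985 at 12% v 10% and 0.96 at 15% v 10% if half the hazard is restricted, and 0.965 and 0.92 if all of it is. The sign follows whichever arm stops more.

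The stakes are limited. The renal endpoints are supportive, lie outside the gatekeeping procedure and carry no multiplicity adjustment. No primary or key secondary conclusion is affected. The change should still be made, because it is cheap and removes the problem.

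**What to change.** In SAP Table 4 and SAP 8.2.2, replace the treatment limit with: at any post-randomization assessment, on or off study drug. Apply this to both the first and the confirming assessment. State in the SAP that this reading governs the matching definitions in protocol 9.5.1.4, including newly developed albuminuria, where the protocol carries the limit and the SAP does not. If an on-drug version is wanted, run it as a labelled sensitivity analysis censored at last dose.

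The cost is a SAP wording change, best made before database lock, plus one extra run if the sensitivity analysis is kept. No new visits or samples are needed, because the off-drug values are already collected. Fixing the reading in the SAP avoids a protocol amendment for this point alone.

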### 8.2.2 Determination of Improvement of Renal function

Time from randomization to first occurrence of 2 consecutive assessments, on scheduled or nonscheduled visits at least 30 days apart, indicative of improvement in renal function (first occurrence of regression of albuminuria or regression of CKD), see Appendix 13.2 for definitions CKD stages. The renal improvement events are defined as;

Regression of albuminuria: defined as when subjects with macroalbuminuria at Baseline develop microalbuminuria or non-albuminuria (ACR < 30  $\mu$ g/mg in spot urine), or subjects with microalbuminuria at Baseline become non-albuminuric, and ACR value decreases  $\geq$  30% from previous assessment during treatment.

Regression of CKD: defined as when a subject with CKD Stage 1 or higher at Baseline improves to normal or lower stages by NKF guideline (eGFR  $\geq$  90 with albuminuria at

Baseline improves to eGFR  $\geq$  90 without albuminuria (ACR < 30 µg/mg in spot urine), or eGFR 60 to 89 at Baseline becomes eGFR  $\geq$  90 with or without albuminuria, or eGFR between 30 to 59 at Baseline improves to > 60 mL/min per 1.73 BSA) during treatment.

#### 8.3 DETERMINATION OF CONVERSION TO T2DM OR TO NORMAL GLUCOSE HOMEOSTASIS

#### **8.3.1** Determination of conversion to T2DM

For the following 2 cohorts, subjects without any type diabetes at Baseline and subjects who are prediabetic at Baseline, as per the definitions in Section 8 above, the time from randomization to conversion to T2DM will be adjudicated as per the CEC Diabetes Adjudication Charter, see Appendix 13.1.4.

For subjects who did not experienced any event, the censoring algorithm is described in Section 8.5.2.2.

#### 8.3.2 Determination of conversion to normal glucose homeostasis

For subjects with prediabetes at Baseline the time from randomization to conversion to normal glucose homeostasis (HbA $_{1c} \le 5.6\%$  and fasting plasma glucose <100 mg/dL without any antidiabetic treatment . The primary analysis will be based on conversion to normal glucose homeostasis that is achieved and maintained through the duration of the study. Sensitivity analyses will include an assessment of 1) any conversion to normal glucose homeostasis at one or more time points during the study and 2) sustained for 2 consecutive measurements separated by 30 days. For subjects who did not experienced any event, the censoring algorithm is described is in Table 7.

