9.7.1.1 Study Endpoints

PRIMARY ENDPOINTS

- Time from randomization to first occurrence of MACE (first occurrence of any of the following events: MI, stroke, or CV death)
- Time from randomization to first occurrence of MACE+ (first occurrence of any of the following events: MACE or hospitalization for unstable angina or HF, or any coronary revascularization) (revised per Amendment 02)

KEY SECONDARY ENDPOINT

(revised per Amendment 02)

- Time from randomization to conversion to T2DM, defined as first occurrence of any component of the 2013 ADA diagnostic criteria¹⁴ in subjects with prediabetes at Baseline. The diagnostic criteria are met if a subject has unequivocal hyperglycemia (random plasma glucose ≥ 200 mg/dL (11.1 mmol/L) with classic symptoms of hyperglycemia or hyperglycemic crisis) OR any of the following criteria are observed and subsequently confirmed on repeat laboratory testing: (revised per Amendments 01 and 02)
 - $\text{HbA}_{1c} \geq 6.5\%$
 - $\text{FPG} \geq 126$ mg/dL (7.0 mmol/L)
 - 2-hour plasma glucose ≥ 200 mg/dL (11.1 mmol/L) by an OGTT

Investigators should make every effort to obtain central lab confirmatory testing no later than 6 weeks after meeting any of the above criteria. Abnormalities of any 1 of the above 3 criteria on repeat testing constitutes diagnostic confirmation of diabetes. Subjects who have been started on anti-diabetic medications following abnormalities in preliminary testing do not require confirmatory testing. (revised per Amendments 01 and 02)

OTHER SECONDARY ENDPOINTS (REVISED PER AMENDMENT 02)

MACE and MACE+ Related: (revised per Amendment 02)

- Time from randomization to first occurrence of each of the individual components of MACE+
- Time from randomization to first occurrence of all-cause mortality

Diabetes and Prediabetes Related (revised per Amendment 02)

- Time from randomization to conversion to normal glucose homeostasis ($\text{HbA}_{1c} \leq 5.6\%$ and fasting plasma glucose < 100 mg/dL without any antidiabetic treatment) in subjects with prediabetes at Baseline (revised per Amendments 01 and 02)
- Time from randomization to conversion to T2DM in subjects without any type of diabetes at Baseline (revised per Amendment 01)
- Change from Baseline in HbA_{1c} at 6 months in subjects with T2DM at Baseline

Renal Related (revised per Amendment 02)

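### The primary rule for conversion to normal glucose requires maintenance to study end, so event status depends on later readings and follow-up length, and withdrawal while normal has no stated status

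*SAP*

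**What the plan says.** The protocol (9.7.1.1, other secondary endpoints) defines the endpoint as "Time from randomization to conversion to normal glucose homeostasis" in subjects with prediabetes at Baseline. Conversion means HbA1c at most 5.6% and FPG below 100 mg/dL without antidiabetic treatment, with no condition that it last. The matching objective (Protocol 8.2, SAP 3.2) concerns conversion at 1 year and yearly thereafter.

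SAP 8.3.2 adds the condition: "The primary analysis will be based on conversion to normal glucose homeostasis that is achieved and maintained through the duration of the study". Two other definitions are sensitivity analyses: "any conversion to normal glucose homeostasis at one or more time points during the study", and conversion "sustained for 2 consecutive measurements separated by 30 days".

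SAP 5.4.3 analyses the endpoint with "a Cox proportional hazards model with factors for treatment and stratification variable". SAP 8.5.2.3 says that "for subjects who experienced an event, their time-to-event will be determined from the randomization date to the date of the event". Its Table 7 censors subjects without an event at completion or at premature discontinuation, including those recorded as "Lost to Follow up".

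Two things are not stated: the date that a maintained conversion carries, and whether a subject who leaves with a normal last reading has maintained it. SAP 8.5 sets each subject's own end of study at the last visit or contact, which would allow a yes. Taken literally, maintenance through the duration of the study suggests a no.

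**The concern.** In a time-to-event analysis, whether the event has happened by a given time should be known at that time, or shortly after if confirmation is needed. Here it is known only at the end of follow-up. The same glycemic course is an event in a subject followed for two years and may be a non-event in one followed for four and a half. The estimated rate then describes the follow-up schedule as well as the glycemia, and no Year 1 result exists at Year 1.

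HbA1c and FPG are scheduled together only at Months 6, 12, 24, 36, 48, EOT and EOS (Protocol Table 4), so a single late reading can decide a subject's status. For subjects who complete treatment, the EOS reading comes about 30 days after the last dose (Protocol 9.1.2.2). The SAP does not say whether it counts towards maintenance.

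The missing withdrawal rule leaves a choice to programming that can move the hazard ratio in either direction.

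**Working it through.** The documents give no event count, power or sample size for this endpoint, so there is no stated figure to reproduce.

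**Inputs from the documents.** 12,000 subjects, 1:1, about 33% prediabetic: 0.33 × 12,000 = 3,960, or 1,980 per arm. Accrual is 15 months and the study lasts 54 months, so planned follow-up is 54 − 15 = 39 to 54 months. Drop-out is 5% per year. Readings are at Months 6, 12, 24, 36 and 48 plus an exit reading.

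**Assumptions.** Each subject moves between non-normal and normal glycemia with yearly rates a (normalisation) and b (relapse): (0.10, 0.6), (0.20, 0.6) and (0.15, 1.5). The process is identical in both arms, so there is no true effect. The second arm's drop-out is set at 5%, 7% or 10% per year.

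**Step 1: what each rule needs to know.** Let a normal run start at reading t_j and let the subject's last reading be t_k. Any conversion is known at t_j. Two consecutive readings are known at t_(j+1). A maintained conversion is known only at t_k.

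**Step 2: dependence on follow-up length, no drop-out.** For a = 0.10, b = 0.6:
- Normal at Month 12, from non-normal at baseline: a/(a+b) × (1 − e^(−0.7)) = 0.1429 × 0.5034 = 0.0719.
- Normal again one year later: (0.10 + 0.6 × e^(−0.7))/0.7 = 0.5685. Six months later: (0.10 + 0.6 × e^(−0.35))/0.7 = 0.7469.
- Study ends at Month 24 (one later reading): 0.0719 × 0.5685 = 4.1%.
- Study ends at Month 54 (readings at 24, 36, 48, 54): 0.0719 × 0.5685³ × 0.7469 = 1.0%.

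Simulation gives the same values, and the pattern holds in all three settings:

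| Rates (a, b) | Maintained, credited by Month 12: end at 24 → end at 54 | Any conversion by Month 12: 24 → 54 | Maintained, rate per 100 patient-years: 24 → 54 |
|---|---|---|---|
| 0.10, 0.6 | 4.1% → 1.0% | 8.4% → 8.1% | 5.5 → 3.1 |
| 0.20, 0.6 | 8.2% → 2.1% | 15.9% → 15.9% | 10.6 → 5.7 |
| 0.15, 1.5 | 1.9% → 0.1% | 10.1% → 10.0% | 4.5 → 2.0 |

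**Step 3: unequal drop-out, no true effect.** There were 400 simulated trials per setting and an unadjusted Cox model. SAP 5.4 drops the CV stratum where the population has no T2DM. Rule A counts a drop-out whose last reading is normal as an event, dated to the start of the final normal run. Rule B allows an event only in subjects observed to study completion and censors drop-outs as in Table 7. The hazard ratio is the higher-drop-out arm over the 5% arm; above 1 means more conversion. Ranges are over the three rate settings.

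| Drop-out per year | Rule A | Rule B |
|---|---|---|
| 5% vs 5% | HR 0.99 to 1.00 | HR 0.99 to 1.00 |
| 7% vs 5% | HR 1.04 to 1.07, rejection 7 to 8% | HR 0.98 to 1.01, rejection 3 to 7% |
| 10% vs 5% | HR 1.09 to 1.15, rejection 16 to 26% | HR 0.95 to 0.98, rejection 3 to 9% |

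At 10% vs 5%, any conversion gives HR 1.02 to 1.03 (rejection 6 to 7%), and two consecutive readings give HR 1.00 to 1.02 (4 to 6%). The two-consecutive runs dated the event to the first of the pair; dating to the second was not simulated. Monte Carlo error is about 1 point on a 5% rejection rate (√(0.05 × 0.95/400) = 0.011) and about 2 points on a 20% rate.

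**The case against.** Several points weigh against the concern. Durability is a legitimate target, and requiring it may have been deliberate. Both alternatives are already pre-specified. The endpoint is outside the gatekeeping procedure (SAP 5.3.3) and is described as supportive, without Type I error correction (SAP 5.4.3). Stopping drug is not leaving the study: Table 4, footnote f, asks for the glycemic profile whatever the drug status, and Protocol 9.5.5.2 expects full withdrawal of consent to be very rare. The only drop-out figure in the documents is 5% per year; any gap between arms is assumed. Using a later reading to confirm an event is also not unusual: conversion to T2DM is confirmed by repeat testing and dated to the first abnormal test (SAP 8.5.2.2). These points limit the importance. They do not remove the dependence on follow-up length, which needs no drop-out, and the wait of weeks or one visit for confirmation differs in degree from a wait of years.

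A reader might infer something stronger: that the arm with more drop-out will appear to convert more, because leaving early produces events. The documents do not support that. It needs Rule A, which the SAP does not state, and the more literal reading (Rule B) reverses the direction. Even under Rule A only the hazard rises; the crude proportion converting does not (11.8% vs 12.5% in the first setting at 10% vs 5%). A reader might also infer that most maintained conversions rest on one final reading. That share depends on how persistent glycemia is between visits, which the documents do not give.

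**Conclusion.** The concern holds in this form: the primary definition makes event status depend on future readings and length of follow-up, departs from the protocol endpoint, and cannot serve the yearly objective. The event date and the status of withdrawals are undefined.

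The follow-up effect is large on the event rate: conversions credited by Month 12 fall to about a quarter or less when the study ends at Month 54 rather than Month 24. With equal follow-up in both arms and no true effect, this alone does not bias the hazard ratio. Bias needs unequal drop-out. Its direction is set by the unstated rule, and its size is about nil at equal drop-out, small at a 2-point gap and material at 5 points under Rule A. These sizes rest on assumed transition rates and assumed differential drop-out. Importance is low to moderate, since no confirmatory claim depends on this endpoint.

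**What to change.** Make the second sensitivity definition in SAP 8.3.2 the primary analysis: two consecutive assessments at least 30 days apart, each with HbA1c at most 5.6% and FPG below 100 mg/dL, without antidiabetic treatment. Write at least 30 days, because most scheduled readings are 6 to 12 months apart. State the event date, preferably the confirming assessment, so that no later reading decides the event; yearly cumulative incidence can then be read directly. Keep any conversion as a sensitivity analysis. Report maintenance to the last assessment descriptively, stating how withdrawals and the EOS reading are handled.

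This swaps analyses already specified, needs no new data, and matches the SAP's own rule for renal improvement (8.2.2). The cost is that durability to study end becomes descriptive, and a single normal reading at the last assessment no longer counts. If the sponsor keeps the maintained definition as primary, the minimum is to state its event date and the status of subjects who withdraw while normoglycemic before unblinding.
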